5.3 Clinical procedures and training

[figure not shown]
Study procedure and device training

Device application using the ITN

Participants will be trained on how to use the ITN properly.

Shortly thereafter, participants will be instructed to place the tips of the ITN into both nostrils simultaneously (Figure 2). Participants will be asked to apply and control the intensity of stimulation by pressing the plus (+) or minus (-) buttons on the device. The level of intensity will be chosen and controlled by the participant. The level of intensity used may be between 2 and 5 out of a possible 5 levels. Each participant will be asked to apply application for 1 minute should no change in discomfort been noted after 1 minute and 3 minutes. Participants will also be told they can control the location of stimulation by the depth and angle of insertion until they feel a “tickle” sensation. Participants will be told they can cease stimulation by pressing the minus button on the Base Unit or by withdrawing the entire ITN device from the nostrils.

Patients will use the TrueTear® a minimum of at least twice a day. The patient is allowed to use it more often than twice a day if needed.

**Figure 2: Use of the TrueTear® Intranasal Neurostimulator (ITN).
Turning on the device and placing it into the nose**

5.4 Quality control and quality assurance

The collection of accurate, consistent, complete, and reliable data will be assured through the use of training sessions, monitoring of the investigator by qualified personnel, data verification, and cross-checking.

6. BIOSPECIMEN COLLECTION (IF APPLICABLE)

6.1 Specimen preparation, handling, and shipping: N/A

6.2 Instruction for specimen preparation, handling and storage: N/A

6.3 Specimen shipment: N/A

6.4 Future use of stored specimens: N/A

7. STUDY PROCEDURES

7.1 Screening/Baseline Procedures

Prospective participants, as defined by the inclusion/exclusion criteria, will be considered for entry into this study. Concurrent enrollment of subjects who are participants in other studies will be allowed based on the investigator's discretion.

During the consent process, study design and treatment regimen will be discussed with each subject. Written informed consent will be obtained before any study specific procedures are performed. However, standard of care clinical information (such as: medical history, BCVA, TBUT, staining, and Schirmer's test) obtained during a subject's clinical visit within the previous 48 hours can be used during the screening visit to determine eligibility and as their baseline assessments.

The following evaluations and procedures will be performed for all subjects during the screening period:

- Written informed consent
- Record of current ocular and systemic medications
- Record of significant medical/surgical history in the past 5 years
- Record of demographic data, including date of birth, sex, and race/ethnicity
- Eye examination (best corrected visual acuity, slit-lamp biomicroscopy, intraocular pressure)
- Corneal fluorescein staining
- Conjunctival lissamine green staining
- Tear break-up time (TBUT)
- Corneal *in vivo* confocal microscopy (IVCM)
- Ocular Surface Disease Index (OSDI) questionnaire
- Ocular Pain Assessment Survey (OPAS) questionnaire
- IDEEL QoL Questionnaire
- The following evaluations and procedures will be performed for all subjects during the Enrollment/Baseline procedures (once the patient is confirmed to be eligible): Visual Analogue Scale (VAS) questionnaire before and after each of the five tests (filter glasses response, hyperosmolar saline response, cold saline response, proparacaine challenge test) Schirmer's test II (with anesthesia)

The description of the procedures is as follows:

Ocular Surface Disease Index (OSDI) questionnaire: (Appendix I) 12-item questionnaire designed to provide a rapid assessment of the symptoms of ocular irritation consistent with dry eye disease and their impact on vision-related functioning. The 12 items of the OSDI questionnaire are graded on a scale of 0 to 4, where 0 indicates none of the time; 1, some of the

Tufts Medical Center

time; 2, half of the time; 3, most of the time; and 4, all of the time. The total OSDI score is then calculated on the basis of the following formula: OSDI= [(sum of scores for all questions answered) x]/[(total number of questions answered) x 4].

Ocular Pain Assessment Survey (OPAS): OPAS Questionnaire (Appendix III): 27-item quantitative questionnaire designed to provide an assessment of the symptoms and quality of life effect of ocular pain. The 27 items of the OPAS questionnaire are graded on a scale of 0 to 10, or 10 to 100, where 0 indicates none and 10 or 100 indicate maximum. This questionnaire should take approximately 2-3 minutes to complete.

Visual Analogue Questionnaire: (Appendix IV) Symptoms of ocular comfort and dryness will be graded for each eye on a scale of 0-100, where 0=extremely uncomfortable, extremely dry and 100=excellent comfort, no dryness. An average rating will be provided for the morning, afternoon and evening. This questionnaire should take approximately 2-3 minutes to complete.

IDEEL QoL Questionnaire (Appendix V): This is a 27-item questionnaire, designed specifically for DED and is divided into three parts. It assesses the quality of life in three aspects of life for the previous 2 weeks: daily activities, work and feelings. The quality of life is assessed on a scale of 0-5, with zero being inability to do the activity. The score is calculated between 0 – 100 with higher scores indicating a better quality of life. This questionnaire should take about 5-10 minutes complete.

Filter glasses: This test will be done in a dimly lit room, about 50 lumens of light intensity (approximately 50-75 square feet room with 10 lumens per square feet), room temperature, pressure and humidity. Each eye will be assessed separately. The other eye will be covered with an occluder to eliminate exposure to the light. The study eye will be covered using a 100% opaque filter and then the opacity of the filters will be reduced in decrements of 10%. Ten graded filters have been developed for this purpose; each of these filters decrease light opacity by 10%. Light will be shone at a distance of approximately 10 cm from the eye, using a mussel light (halogen fiber-optic transilluminator). Starting at the 100% opaque filter, the filter at which the patient starts to feel pain/photophobia will be noted. That light level will be used to assess threshold and a pain/photophobia for each filter will be noted on a scale of 1-10. Using pilot studies we have seen that the pain/burning can increase with an increase in light in patients with NCP.

Cold Response Test: One drop of cold 0.9% preservative-free saline eye drops will be topically applied onto the patient's eyes. The level of discomfort/pain will be assessed by the VAS questionnaire before and after the drops are applied.

Hyperosmolality Response: One drop of 5% sodium chloride (Muro 128® 5%) drop will be topically applied on the conjunctival fornix of both eyes. The level of discomfort will be measured the VAS questionnaire before and after application of a 5% sodium chloride drop.

Proparacaine Challenge Test: One drop of Proparacaine Hydrochloride Ophthalmic Solution 0.5% will be topically applied in both eyes to differentiate between the peripheral versus central

Tufts Medical Center

component of the patient's pain or discomfort. The level of discomfort/pain will be assessed by the VAS questionnaire.

Schirmer's (II) Test with Anesthesia: The Schirmer's test will be performed 3 minutes after a drop of topical anesthesia with 0.5% proparacaine (Alcon Inc., Ft Worth TX) is applied to the eye. The Schirmer test is performed by placing a narrow filter-paper strip (5 x 35 mm strip of Whatman #41 filter paper) in the inferior cul-de-sac. This test is to be conducted in a dimly lit room. The subject should gently close their eyes until five minutes have elapsed and the strips are removed. Since the tear front will continue advancing a few millimeters after it has been removed from the eyes, it is important to mark the tear front with a ball-point pen at precisely five minutes. Aqueous tear production will be measured by the length in millimeters that the strip wets during 5 minutes. This procedure should take approximately 10 minutes to complete.

Tear Break-Up Time (TBUT): The standard TBUT measurement will be performed by dropping a fluorescein drop to the inferior tarsal conjunctiva. After several blinks, the tear film will be examined using a broad beam of the slit lamp with a blue filter. The time lapse between the last blink and the appearance of the first randomly distributed dark discontinuity in the fluorescein stained tear film will be measured three times and the mean value of the measurements will be calculated. The tear break-up time will be evaluated prior to the instillation of any eye drops and before the eyelids are manipulated in any way. Break-up times less than 10 seconds are considered abnormal. A positive change from baseline indicates improvement. This procedure should take approximately 10 minutes total to complete.

Corneal Fluorescein Staining: (Appendix II) Corneal fluorescein staining will be performed after 3 minutes of application of a fluorescein drop. The entire cornea will be then examined using slit-lamp evaluation with cobalt blue illumination. Staining will be graded using the NEI grading scheme, with a total range of 0-15.

Conjunctival Lissamine Green Staining: (Appendix II) Grading of conjunctival lissamine green staining will be performed after 2 minutes of application of a lissamine green drop. The nasal and temporal conjunctiva will be examined using slit-lamp evaluation with white light. Staining will be graded using the NEI grading scheme, with a total range of 0-18. This procedure should take approximately 2 minutes to complete.

In Vivo Confocal Microscopy (IVCM): *In vivo* confocal microscopy (IVCM) is a new imaging method, which allows visualization of the corneal structures at the cellular level. With a magnification of 800 times, it makes it possible to detect and quantify changes in the epithelial layers and sub-basal nerve plexus.

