3.0 STUDY DESIGN

3.1. Study Design Description

This study is a prospective, interventional, open-label, single arm, non-randomized trial treating 45 patients with peripheral or mixed neuropathic corneal pain at their baseline exam and following 45 days and 90 days of daily use with the TrueTear™ ITN device.

3.2 Statistical analysis:

Two-tailed paired sample t-test and Pearson correlation will be performed for pain intensity, and to assess associations between different quality of life scores. Statistical comparisons of the mean values between different groups based will be performed using ANOVA.

The normality of continuous variables will be tested with the Shapiro-Wilk test. All tests will be two tailed and statistical significance will be considered for p values of less than 0.05.

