10. STATISTICAL METHODS/DATA ANALYSIS

10.1 Primary endpoint(s) or outcome measure(s)

- Change to overall pain by the Visual Analogue Scale (VAS) after ITN stimulation

10.2 Secondary Outcome Measures:

- Change to overall pain by the Visual Analogue Scale (VAS) after daily ITN stimulation over 45-day period.
- Change to overall pain by the Visual Analogue Scale (VAS) after daily ITN stimulation over 90-day period.
- Change in quality of life as measured daily with OPAS and IDEEL
- Safety
- Tolerability
- Change in response to hypertonic solution
- Change in response to proparacaine challenge test
- Change in the intraocular pressure (IOP) measured in each visit.
- Reduction on other concomitant pain therapy

10.3 Sample Size Determination:

There is no existing systematic epidemiological study regarding the neuropathic corneal pain and there are no studies available to determine the population sample needed to detect differences between patients before and after the neuro stimulation for neuropathic corneal pain. However, based on a recent preliminary observations in 5 patients with concurrent NCP and dry eye disease, and the decrease in pain levels immediately after the use of ITN, we would achieve 80% power with an alpha error of 0.05 for pain scale intensity of 1-10, and assumption of 50% decrease in pain levels, for a sample size of 25 patients. The enrollment of 30 patients with NCP would compensate for potential dropouts.

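### Section 7.1 describes the VAS as a comfort-and-dryness rating, while 10.1 and 10.2 take overall pain from it, so the primary instrument must be reconciled with the primary endpoint

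*Combined protocol and SAP*

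**What the plan says.** Section 7.1, in its paragraph on the Visual Analogue Questionnaire, reads: "Symptoms of ocular comfort and dryness will be graded for each eye on a scale of 0-100, where 0=extremely uncomfortable, extremely dry". The upper anchor, 100, is excellent comfort with no dryness. The paragraph asks for an average covering morning, afternoon and evening.

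Section 10.1 has one primary endpoint: "Change to overall pain by the Visual Analogue Scale (VAS) after ITN stimulation". Section 10.2 adds "Change to overall pain by the Visual Analogue Scale (VAS) after daily ITN stimulation over 45-day period" and "Change to overall pain by the Visual Analogue Scale (VAS) after daily ITN stimulation over 90-day period". Section 3.2 states the test: "Two-tailed paired sample t-test and Pearson correlation will be performed for pain intensity". Section 10.3 sizes the trial on a "pain scale intensity of 1-10, and assumption of 50% decrease in pain levels", without naming the VAS.

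The VAS is also used elsewhere. Inclusion criterion 5 in 4.1 uses it for relief of pain or discomfort after proparacaine. The challenge tests in 7.1 use it for discomfort (hyperosmolar saline) or for discomfort and pain together (cold saline, proparacaine). Section 7.4, Study Specific Procedures, lists a VAS after ITN and, on a separate line, the ITN response at 1 and 3 minutes for pain and light sensitivity. Only the heading of Appendix IV, which holds the form, can be read.

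**The concern.** The primary endpoint is named as pain, but the instrument it cites is described as measuring something else. This matters more here than in most pain trials. Section 5.1 describes the device as activating nerves that drive natural tear production, so a rating anchored on dryness may improve through tears alone. The hypothesis in section 2.0 is that stimulation blocks ocular pain signalling. With a single arm and no control group, nothing in the design would show that a dryness effect had been reported as a pain effect.

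Section 10.1 also does not say which post-stimulation reading counts, and the scale in 10.3 differs from the one in 7.1 in both range and direction.

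**Working it through.** The point is mainly textual, so the passages are set side by side first.

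| Feature | 7.1, VAS paragraph | 10.1 and 10.2 | Other places |
|---|---|---|---|
| Construct | Comfort and dryness | Overall pain | Pain or discomfort (4.1, criterion 5); discomfort, or discomfort and pain (7.1 challenge tests); pain intensity (3.2) |
| Timing | Average by part of day | After stimulation; over 45 and 90 days | Before and after each test (7.1 list); VAS after ITN, and response at 1 and 3 minutes (7.4) |
| Unit | Each eye | Overall | Patients are counted in 10.3 |
| Scale | 0-100, higher is better | Not stated | 1-10 pain intensity (10.3) |

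1. **Construct.** No readable passage defines a second VAS. The diary in Appendix VII gives discomfort and pain separate lines, so the protocol does not treat them as one quantity throughout. The conflict between 7.1 and 10.1 is direct.

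2. **Timing.** A day-part average cannot express a response to an in-office stimulation (7.2). The 7.1 procedure list and 7.4 point to immediate readings, so the intent is fairly clear. What remains open is whether the 1-minute or the 3-minute reading is primary. That these are VAS readings is an inference from the neighbouring 7.4 entry. For days 45 and 90, a momentary rating or a day average would each be coherent, and 10.2 does not choose.

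3. **Unit.** The word overall in 10.1 and the patient counts in 10.3 imply one score per patient. The missing link from per-eye ratings to that score is mostly an omission.

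4. **The plan's own figure.** Section 10.3 gives 25 patients for 80% power at alpha 0.05. It gives no baseline mean and no SD of change, so 25 can only be back-solved:
   - Normal approximation, two-sided: (1.960 + 0.842)/√25 = 0.560 SD of change. The paired t-test gives 0.584.
   - Assuming baseline pain of 4 or 8, a 50% fall is 2 or 4 points. The SD of change that makes 25 correct is then 2/0.584 = 3.4 or 4/0.584 = 6.8.
   - So 25 can be neither confirmed nor refuted.

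5. **Does the 50% assumption carry over to the 7.1 scale?** Assume, for illustration only, comfort = 100 − 10 × pain. Halving pain then gives:
   - pain 4 to 2: comfort 60 to 80, a rise of 20/60 = 33%;
   - pain 6 to 3: comfort 40 to 70, a rise of 30/40 = 75%;
   - pain 8 to 4: comfort 20 to 60, a rise of 40/20 = 200%.

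   One fixed percentage on the pain scale is not one percentage on the comfort scale. A linear change of range or direction does not by itself alter the paired t-test. It matters for percentage statements, such as those in 10.3 and criterion 5.

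6. **Reach.** Overall pain on the VAS is the primary outcome and two of the nine secondary outcomes: 1 + 2 = 3 of 10.

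**The case against.** The strongest reply is that the form itself is not visible. If Appendix IV carries a pain item, the 7.1 paragraph is merely an incomplete description and the substitution of comfort for pain does not occur. Sections 4.1, 7.1 (challenge tests) and 10.1 all use the VAS for pain or discomfort, against one descriptive paragraph. This stands as a limit on the harm. It does not remove the conflict, because 7.1 would still misdescribe the primary instrument and 10.1 would still not name the item or the reading.

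Several stronger readings are tempting but not supported:

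- *That the trial does not measure pain.* OPAS and the diary both record it. Section 10.1 simply does not name them.
- *That the challenge-test outcomes fall with the primary.* Section 10.2 lists only "Change in response to hypertonic solution" and "Change in response to proparacaine challenge test", neither of which claims pain. The hyperosmolar test is rated as discomfort, which fits the 7.1 anchors.
- *That staff would use day-part averages for the acute readings.* The more specific instructions in 7.1 and 7.4 point to immediate ratings.
- *That the false-positive rate is inflated by pooling two eyes or picking the better reading.* No section proposes either analysis and no correlations are given, so an error rate would be conjecture.

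**Conclusion.** The VAS paragraph in 7.1 is wrong as written for the use that 10.1 and 10.2 make of it. The firm part is the construct conflict, which reaches three outcomes including the only primary one. The open choice of reading time in 10.1 and the mismatch of scale with 10.3 are secondary. No numerical size can be put on the construct conflict, because the documents hold no VAS data. The percentage conversions rest on an assumed mapping and show only that the scales are not interchangeable.

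Confidence is moderate, since the Appendix IV form is unseen. A reader might infer that the sample size is wrong; the documents do not allow that conclusion either way.

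**What to change.** - **7.1:** Correct the VAS paragraph so that the VAS used for 10.1 and 10.2 is an overall pain-intensity item giving one score per patient. For the primary endpoint, have it rated immediately before and after the in-office stimulation. If Appendix IV already has such an item, describe it; if not, add one line to the form.
- **10.1:** Name that item, and state which of the already planned readings, 1 minute or 3 minutes, is primary.
- **10.2:** Name the same item for days 45 and 90, and state whether the rating is momentary or a day average.
- **10.3:** Express the assumed decrease on the same scale.
- **Comfort and dryness:** Report these separately from pain.
- **Criterion 5:** Reconcile the VAS wording in 4.1, the 7.1 VAS paragraph and the 7.1 proparacaine test, so that the item and the basis for percentage relief are unambiguous.

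The cost is protocol wording and at most one form line, with no added visit, procedure or patient. The change makes the endpoint a pain score. In a single-arm trial it cannot separate pain relief that comes through tears from a direct neural effect.

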7.2 Study Visit

The study will be performed in four visits. During the baseline visit, all patients will be evaluated using the flowchart (page 2). The first visit will include in-office testing of ITN and response to ITN. After 45 days (6 weeks \pm 1 week) and 90 days (3 months \pm 2 weeks) of using the ITN on a daily basis, the patients will return for follow-up visits. The same flowchart as for screening visit will be followed in these two visits (with the exception confocal microscopy on visit 2). Additionally, evaluation of diary for daily use (Appendix VII) and questionnaires regarding

Tufts Medical Center

tolerability and safety of device and any reduction in the use of concomitant pain medications will be assessed on these visits.

7.3 Standard of Care Procedures

The following procedures are the standard of care:

- Ocular Surface Disease Index Questionnaire (OSDI)
- OPAS
- VAS
- Eye examination (best corrected visual acuity, bio-microscopy, intraocular pressure measurement)
- Schirmer's II test (may be study specific)
- Tear break-up time (TBUT)
- Corneal fluorescein staining
- Conjunctival lissamine green staining
- Central corneal *in vivo* confocal microscopy

7.4 Study Specific Procedures:

At the study visit, the following procedures will be performed for study specific purposes in addition to standard of care procedures:

- Questionnaires: OPAS, VAS after ITN, IDEEL, Safety and tolerability questionnaires
- ITN response at 1 minute and 3 minutes to assess pain and light sensitivity
- Diary to keep readings (Appendix VII)
- Schirmer's test with anesthesia (may be standard of care)
- Filter glasses test
- Cold saline solution response
- Hypertonic saline solution response
- Proparacaine challenge test (may be standard of care)

7.4 Follow-up Procedures

Subjects will come back for a 1st visit after the screening visit; 2nd visit at 45 days (\pm 1 week) following the first visit, and 3rd visit following 90 days after the first visit (\pm 2 weeks). All of the procedures done at the baseline visit will be done in the 2nd and 3rd visits (see flowchart).

In addition, subjects will be asked about their usage of the ITN. Ocular safety and tolerability questionnaire (appendix VI) will be administered in the 2nd and 3rd visit. The subject will be asked to complete a diary every day to record any pain symptoms (Appendix VII). The subject will be asked to send their pain diary weekly to the study coordinator, in however method works for the subject to ensure compliance with the ITN. They will also need to bring the diary to each study visit, to ensure compliance.

Ocular Tolerability Questionnaire (Appendix VI): This questionnaire assesses tolerability of the ITN device. It assesses symptoms of discomfort in each eye after ITN use.

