4.0 SUBJECT SELECTION

4.1. Subject Inclusion Criteria:

1. Age ≥ 22 .
2. Ability to consent to study.
3. Symptoms of neuropathic corneal pain for at least 3 months, such as burning, stinging, light sensitivity, discomfort or pain.
4. Positive *in vivo* confocal microscopy (IVCM) findings for NCP such as presence of microneuromas and decreased nerve density. The presence of positive IVCM findings serves in lieu of skin biopsies as proof of nerve injury.
5. Fifty percent or more relief of pain or discomfort after instillation of Proparacaine eye drops as measured by the Visual Analogue Scale (VAS).

4.2. Subject Exclusion Criteria:

1. Clinically significant acute ocular surface diseases, such as active infectious keratitis or recent ocular surgery in the past 3 months.
2. Chronic or recurrent epistaxis, coagulation disorders.
3. Nasal or sinus surgery or significant trauma to the nose.
4. Severe nasal airway obstruction or vascularized nasal polyps.
5. Cardiac demand pacemaker, implanted or wearable defibrillator, or other implanted electronic device in the head or neck.
6. Chronic or recurrent nosebleeds
7. Bleeding disorder or another condition that can lead to increased bleeding
8. Known hypersensitivity (allergy) to the hydrogel material that contacts the nasal mucosa
9. Disabling arthritis, neuropathy, or limited motor coordination affecting self-handling of the device.
10. Allergic to benzalkonium chloride (the Co-Investigators who administer the eye drops ask all patients if they are allergic to any eye drop preservatives before proceeding with the eye drops)

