Appendix VI: Ocular Tolerability and Compliance Questionnaire

After you used the TrueTear® neurostimulation, how intensely have you experienced the following symptoms?

Itching

Right Eye:	None	Trace	Mild	Moderate	Severe
Left Eye:	None	Trace	Mild	Moderate	Severe

Burning Sensation

Right Eye:	None	Trace	Mild	Moderate	Severe
Left Eye:	None	Trace	Mild	Moderate	Severe

Foreign Body Sensation

Right Eye:	None	Trace	Mild	Moderate	Severe
Left Eye:	None	Trace	Mild	Moderate	Severe

Have you experienced any other symptoms after undergoing the study tests?

YES NO

If yes, which one(s) _____

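### Appendix VI grades tolerability only at days 45 and 90, so without a matching pre-device grade or a control arm its scores cannot be cleanly separated from the patient's own disease

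*Combined protocol and SAP*

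**What the plan says.** Section 10.2 lists tolerability among nine secondary outcomes without defining it. Section 10.6 adds only that directed questioning will be used, and section 5.2 names Appendix VI as the form for directed questioning, without tying it to a visit.

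Timing comes from section 7.4 (Follow-up Procedures): "Ocular safety and tolerability questionnaire (appendix VI) will be administered in the 2nd and 3rd visit". The same section gives the form's purpose: "It assesses symptoms of discomfort in each eye after ITN use". Section 7.2 agrees: it places at the day-45 and day-90 visits questionnaires on "tolerability and safety of device and any reduction in the use of concomitant pain medications will be assessed on these visits". Section 7.4 (Study Specific Procedures) lists "Questionnaires: OPAS, VAS after ITN, IDEEL, Safety and tolerability questionnaires" for the study visit but does not say which visit.

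The stem of Appendix VI refers to the time after device use and asks "how intensely have you experienced the following symptoms". Itching, burning and "Foreign Body Sensation" are each graded per eye in five steps from None to Severe. No recall period is stated. The closing item, answered yes or no with free text, is about the study tests and not the device: "Have you experienced any other symptoms after undergoing the study tests".

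Section 4.1, criterion 3, requires "Symptoms of neuropathic corneal pain for at least 3 months, such as burning, stinging, light sensitivity, discomfort or pain". Section 3.1 describes a single-arm trial.

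**The concern.** A tolerability measure should show what the device adds. Here one of the three graded symptoms, burning, is among those that qualify a patient for the trial, and the form is first completed after about six weeks of daily use. The stem fixes the time of the symptom but does not ask whether it is new or worse than before. With no comparator, a moderate burning grade at day 45 could be the burning the patient enrolled with, burning caused by the device, or the net of some relief and some irritation.

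What is at stake is the interpretation of one secondary outcome and of the tolerability part of the 90-day safety aim. The primary endpoint, change in VAS pain after stimulation, is not touched. A matched pre-device grade cannot be recovered once stimulation has begun.

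**Working it through.** The plan states no tolerability rate, cut-off, sample size or power, so it has no figure of its own to reproduce. The check has two parts.

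**1. What pre-device information exists for each graded symptom**

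| Appendix VI item | Named in section 4.1? | Pre-device reading elsewhere | Same scale? |
|---|---|---|---|
| Burning, per eye, intensity | Yes | OPAS item 23 at screening, repeated at follow-up and in the daily diary | No: how often burning accompanies eye pain, 0 to 100%; Appendix III refers to the worse eye |
| Foreign body sensation, per eye, intensity | No | OSDI item 2 (gritty eyes) at screening, repeated at follow-up | No: frequency 0 to 4, not per eye |
| Itching, per eye, intensity | No | None in any questionnaire reproduced in the documents | Not applicable |

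The first diary page (Appendix VII) takes readings before and after device use, but of discomfort, pain and photosensitivity. None of these is an Appendix VI item.

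**2. How far background symptoms could move the result**

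The inputs below are assumptions, since the documents give no rates. Let b be the share of patients with disease burning at the grade of interest, d the share of the remainder in whom the device newly causes it, and r the share of those with disease burning in whom the device relieves it. The share shown on the form is

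observed = b(1 − r) + d(1 − b).

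*No device effect (d = 0, r = 0).* The expected count is N × b. Section 10.3 enrols 30 and section 3.1 says 45, so both are shown. (The two figures need reconciling, but nothing here depends on which is right.) For b = 20%, 40%, 60% and 80%:

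- N = 30: 6, 12, 18, 24 patients
- N = 45: 9, 18, 27, 36 patients

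*New burning in 10% of the rest (d = 10%).* The last column is the relief rate above which the observed share falls below b although the device is causing burning, that is r > d(1 − b)/b.

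| b | Observed with r = 0 | Newly caused | Pre-existing share of observed | Relief rate that masks it |
|---|---|---|---|---|
| 20% | 20 + 8 = 28% | 8 points | 20/28 = 71% | 8/20 = 40% |
| 40% | 40 + 6 = 46% | 6 points | 40/46 = 87% | 6/40 = 15% |
| 60% | 60 + 4 = 64% | 4 points | 60/64 = 94% | 4/60 = 6.7% |
| 80% | 80 + 2 = 82% | 2 points | 80/82 = 98% | 2/80 = 2.5% |

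*Sensitivity to d, with b = 30% and r = 0.* If d = 5%, observed = 30 + 3.5 = 33.5%, of which 3.5 points are new. If d = 50%, observed = 30 + 35 = 65%, of which 35 points are new, more than half. The mix therefore depends on rates that Appendix VI, as scheduled, cannot supply.

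**The case against.** The strongest reply is that the plan is not blind to starting symptoms. OPAS and OSDI are taken at screening and repeated at visits 2 and 3, so OPAS burning can be compared with OPAS burning, and grittiness with grittiness, within the same patient. The second diary page repeats OPAS item 23 daily. Adverse events are queried at every visit, and the Appendix VI stem does refer to the time after device use. All of this stands, and a reader who inferred that the trial has no pre-device information on these symptoms would be wrong. What remains is that those scales measure frequency, do not give a per-eye grade, and leave itching with no baseline.

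A reader might also infer that disease symptoms will be counted as device intolerance. The documents do not support that: neither section 10.2 nor section 10.6 turns answers into intolerance. Nor do they support saying that the result would mostly describe the disease. That follows only if the device rate is assumed to be small, and relief would push the error the other way.

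The overlap with eligibility is also limited. Criterion 3 gives burning as one example, does not require it, and does not name itching or foreign body sensation.

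On early stoppers, section 7.6 ends study procedures for those who withdraw and section 5.2 allows them to be replaced, so withdrawal before day 45 leaves no Appendix VI grade. It does not follow that they leave no trace. Adverse event records and the diaries sent in weekly may capture them, and stopping the device is not the same as leaving the study.

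**Conclusion.** The concern holds in a limited form. On Appendix VI alone, a follow-up grade cannot be cleanly attributed to the device, and the direction of the error is unknown. The problem is clearest for burning, which is an entry symptom, and least repairable for itching, which has no other baseline reading. For burning and grittiness a rough within-patient check is possible on other scales.

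The size cannot be fixed from the documents. On assumed background rates of 20% to 80%, between 6 and 24 of 30 patients, or 9 and 36 of 45, would report burning with no device effect at all. These are illustrations and not estimates.

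The reading of the schedule rests on the prose of sections 7.2 and 7.4. The flowchart that section 7.2 cites is not part of the text available here. If it shows a completion before first use, the point reduces to bringing the prose into line with it. As it stands, this is a worthwhile change to one secondary outcome of a pilot trial, and it does not affect the primary endpoint.

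**What to change.** In section 7.4 (Follow-up Procedures), give the three graded items at visit 1, before any drop challenge and before the first stimulation, and again after the in-office use. The order matters: the saline and proparacaine tests could themselves alter burning and foreign body sensation. State the same order for visits 2 and 3, where those tests are repeated.

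In Appendix VI, keep the per-eye five-step scale, word the three items without reference to the device, and add a recall period. Use that wording and recall period both before first use and at visits 2 and 3, because a baseline question that differs from the follow-up question would not be a matched reading. The reading after the in-office use can only cover the time since stimulation, so report it separately as the immediate response.

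In section 10.2, report tolerability per symptom as the share of patients whose grade worsens from the pre-device reading, alongside the raw grades. State how many patients withdrew before day 45 and so have no follow-up grade, and what their adverse event and diary records show.

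The cost is two extra completions of a short form at a visit already scheduled, a few more minutes for the patient, and a small wording change to the form and to sections 7.4 and 10.2. No extra staff or procedure is needed.
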